## A. AIMS OF THE STUDY

Refugees in low-and middle-income countries are at risk of unhealthy alcohol and other drug (AOD) use, yet few receive treatment. Through funding from Elrha/R2HC, we aim to conduct a randomized controlled trial to evaluate the effectiveness and implementation of stepped-care AOD services (screening, brief intervention, and referral to evidence-based psychotherapy; SBIRT) for Congolese refugees and host community members in Mantapala, an integrated settlement in northern Zambia.

The study is being conducted in collaboration with local partners in Zambia: Women in Law and Development in Africa (WiLDAF), United Nations High Commissioner for Refugees (UNHCR), University of Zambia, and CARE Zambia.

The procedures described in this protocol build on a formative research study, which was previously approved by the CUMC IRB (Protocol: AAAT1592) and the University of Zambia Biomedical Research Ethics Committee. The specific aims of the research described in this protocol include:

- 1. To evaluate the effectiveness of an SBIRT stepped-care system in reducing unhealthy AOD use among refugees and the host community. We will employ a hybrid Type I effectiveness implementation trial evaluating the effectiveness and implementation of the SBIRT stepped-care system in an integrated refugee setting.
- **2. To explore the implementation of the SBIRT stepped-care system.** We will conduct in-depth interviews with participants, intervention counselors, implementing agency staff, policymakers, and other stakeholder to examine the SBIRT system's potential for scale-up, affordability, and sustainability within an integrated refugee-host community setting.

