#### C. OVERVIEW OF STUDY DESIGN

Describe the methodology that will be used in this study, covering such factors as retrospective vs. prospective data collection, interventional vs. non-interventional, randomized vs. non-randomized, observational, experimental, ethnography, etc.

The study design involves a randomized controlled trial evaluating effectiveness (e.g., alcohol use, mental health; Aim 1) and implementation (e.g., scalability; Aim 2) of the SBIRT system of care for alcohol and other drug use problems in Mantapala refugee settlement in Luapula Province, which is located in northern Zambia. We will enroll 400 participants into the RCT; half will be randomly assigned to receive SBIRT and half will be randomly assigned to receive treatment as usual (TAU). We will evaluate self-reported alcohol, substance use, and mental health outcomes via audio computer-assisted self-interviewing (ACASI) at three timepoints: baseline, 6 months post-baseline, and 12 months post-baseline. We will conduct mixed methods interviews with a sub-sample of participants, SBIRT counselors, and humanitarian program and policy officials to explore implementation constructs of intervention acceptability, feasibility, appropriateness, and cost.

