# E.1f Interventions

- SBIRT. All participants randomized to SBIRT will receive an on-the-spot alcohol brief intervention (CETA-BI) and be categorized as low or moderate/high severity. Moderate/high severity is defined as one or more of: (a) AUDIT scores indicating moderate-to-severe AUD (≥12 for women; ≥16 among men); (b) meeting validated symptom criteria for depression (≥16 on CES-D),  (c) trauma/anxiety (≥2.5 on HTQ),  (d) substance use (≥27 on ASSIST).  Participants who are low severity will not receive any additional treatment. Participants who are moderate/high severity will be connected to a CETA counselor and will begin full CETA treatment. This will involve approximately 6-12 weekly CETA sessions. CETA sessions will be conducted in a private setting mutually agreed upon by the counselor and participant (this could be in the health clinic or some other community-based setting where the participant feels comfortable). Data collected for these intervention participants will include the Improving Your Health worksheet (during the BI session), the Client Monitoring Form (during CETA sessions) and the Alcohol Timeline Followback (completed at both the BI and subsequent CETA sessions. All of these measures are included in Rascal.
- TAU. In October 2019, Mantapala health workers and supervisors were trained in mhGAP-HIG, which is a mental health service provision guide for use in humanitarian settings; this training was led by staff from United Nations High Commissioner for Refugees. This training did *not* include evidence-based psychological interventions (e.g., CETA). Participants randomized to TAU will be referred to the existing services that exist in the health clinic located in Mantapala refugee settlement. This clinic is staffed by eight clinical staff who provide clinical assessments, primary care, basic counseling, and limited specialized services (e.g., maternal and child care, HIV treatment). More specialized services are referred to the District Hospital in Nchelenge, which is the nearest town approximately 50 kilometers away.

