### E.3c Interviews

Mixed methods interview guides will be based on the Johns Hopkins Dissemination and Implementation measure, which explores adoption, acceptability, appropriateness, feasibility, scalability, sustainability and reach/access of SBIRT. Interview guides will be adapted to the stakeholder group (SBIRT participant, counselor, other stakeholder), but will cover similar domains. The interview guides include questions assessing these constructs quantitatively using a Likert scale as well as open-ended questions and probes that are adapted over the course of the study. These guides are included in Rascal. While adaptations to the specific questions may evolve over the course of the interviews, if any modifications are made to the questions or probes that extend beyond the constructs described above, we will submit a modification to the IRB. These interviews will be administered by a WiLDAF RA in a private location, or a location requested by the study participant. Implementation interviews will be audio recorded. We expect the interview will take approximately one hour to complete. Interviews with humanitarian stakeholders may take place by phone/Zoom.

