### F. STATISTICAL PROCEDURES

Provide sufficient details so that the adequacy of the statistical procedures can be evaluated including power calculations to justify the number of participants to be enrolled into the study. Definitions of subject terms such as enrolled and accrued as used for Rascal submissions can be found in the Subjects section

The primary outcome is the difference in change in AUDIT score from baseline to 12-month follow-up between SBIRT and TAU. Using baseline data from an ongoing study of CETA-BI + Full CETA in Lusaka, we estimated the sample size required to estimate a moderate treatment effect (Cohen's d=0.5) with 90% power would be 172 (86 per arm). Given the stratified sampling, clustering, planned subgroup analyses, and possible attrition, our study will require a total sample size of 400.

The primary analysis will use mixed effects regression to estimate the difference in change in AUDIT scores between the treatment groups. Secondary analyses will include: a) treatment effectiveness for secondary outcomes; b) moderator/subgroup; c) mediators; d) predictors of treatment completion; e) longitudinal analysis of weekly symptom change (on the CMF and Alcohol TLFB for CETA participants; and g) mixed methods analysis based on best practice guidelines for exploring implementation data.

Qualitative data from the implementation interviews will be transcribed and any identifiable information will be redacted. Once transcribed, the audio recordings will be destroyed. These data will then be analyzed by members of the research team using thematic analysis whereby research staff read the full set of transcripts and develop codes using a subset of those transcripts. Once a codebook has been developed, it will be applied to the full set of transcripts with codes added as needed. We anticipate the main domains will include adoption, acceptability, appropriateness, feasibility, and reach/access of SBIRT.

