- 3) Each participant will be assigned a unique study ID number, and all data (e.g., ACASI data, CMF/TLFB data, implementation data) will be coded with ID numbers only and will not contain identifying information. These data will be stored on the encrypted system with restricted access to essential investigators and staff. We will not obtain signatures on the consent form/information sheet. We will only collect sensitive data/identifying information (names, phone numbers, and addresses) from participants for purposes of contacting participants to schedule study visits. An encrypted spreadsheet linking participant names, phone numbers, and addresses with ID numbers will be stored separately from the coded data. This personally identifiable information will be stored on an encrypted endpoint computer in a locked office within the study office in Kawambwa. Only essential staff for conducting participant follow-ups will have access to this file. Columbia personnel will not have access to sensitive data/identifying information. Following the end of the study, the link and all personally identifiable information will be destroyed such that all data are completely de-identified.
- 4) Paper-based data (Client Monitoring Form, Alcohol TLFB, and Improving Your Health worksheets, and notes taken during qualitative interviews and discussions) will be coded and securely stored in locked file cabinets in the study team's locked offices. They will be entered into an encrypted database stored on an encrypted shared data system.
- 5) Qualitative interviews in Aim 2 will be recorded with permission from the participants (no other activities will have audio recording). Recordings will be destroyed after interviews are transcribed. We expect transcription of audio files to be done within one to two weeks after the interview session. The oral study introduction will not be included in the recording and we will train research assistants to avoid mentioning personal identifying information during the course of the interview. Any personal information that is discussed during the interview will be redacted from study transcripts.

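### Does leaving cost and affordability out of the interview construct list leave part of Aim 2 without data?

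*Combined protocol and SAP*

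**What the plan says.** Two places state what the implementation interviews are for. Aim 2 (section A) names three targets: "potential for scale-up, affordability, and sustainability within an integrated refugee-host community setting". Section C says that interviews with a sub-sample of participants, SBIRT counselors and program and policy officials will "explore implementation constructs of intervention acceptability, feasibility, appropriateness, and cost".

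Two later places give the detail. Section E.3c, under the procedures for implementation interviews, bases the guides on a Johns Hopkins dissemination and implementation measure, "which explores adoption, acceptability, appropriateness, feasibility, scalability, sustainability and reach/access of SBIRT". It adds that the guides are adapted to each stakeholder group, combine Likert items with open-ended questions and probes, and are held in Rascal. If changes are made to "questions or probes that extend beyond the constructs described above, we will submit a modification to the IRB". Section F says of the thematic analysis: "We anticipate the main domains will include adoption, acceptability, appropriateness, feasibility, and reach/access of SBIRT". Once the codebook exists, "it will be applied to the full set of transcripts with codes added as needed".

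The other trial data described are the ACASI questionnaires, the forms used in the SBIRT arm ("Data collected for these intervention participants will include the Improving Your Health worksheet (during the BI session), the Client Monitoring Form" and the Alcohol Timeline Followback) and the exit interviews on accuracy of self-report. None is described as recording cost or resource use.

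**The concern.** The protocol promises affordability once and cost once, and both times the interviews are the source. The section a research assistant would work from lists seven constructs and omits both. The section an analyst would work from lists five domains and omits both. No other instrument is described as a fallback.

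The omission also looks selective. E.3c does carry scalability and sustainability, the other two targets of Aim 2, so the list cannot be dismissed as a loose summary that left out all of Aim 2's language. The ethics clause gives the list some force, since questions added later that go outside it would need a modification. If the guides really contained no cost questions, one of Aim 2's three targets would rest on what interviewees happened to volunteer. Stepped care is motivated partly by scarce resources (section B), so that would be a real loss to the implementation aim.

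**Working it through.** There is no statistical figure to reproduce. The check compares lists, counting affordability and cost as one construct.

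| Place | Constructs named | Affordability/cost? |
|---|---|---|
| Section A, Aim 2 | scale-up, affordability, sustainability (3) | yes |
| Section C | acceptability, feasibility, appropriateness, cost (4) | yes |
| Section E.3c, implementation interviews | adoption, acceptability, appropriateness, feasibility, scalability, sustainability, reach/access (7) | no |
| Section F, anticipated domains | adoption, acceptability, appropriateness, feasibility, reach/access (5) | no |
| Section F, lettered secondary analyses | a, b, c, d, e, g (6) | not named |

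**Promised set.** 3 + 4 − 1 (affordability/cost counted once) = 6 distinct constructs.

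**Carried into E.3c.** 6 − 1 = 5, reading scale-up as scalability. Affordability/cost is the only one missing: 1 of Aim 2's 3 targets and 1 of section C's 4.

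**Carried into the section F domains.** Of the seven E.3c constructs, 7 − 5 = 2 are absent: scalability and sustainability.

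The counts are therefore right. What they imply depends on how each list is meant to be read.

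1. *Section C is part of the plan.* It says outright that the mixed methods interviews will explore cost. Cost is thus a stated interview construct in the protocol taken as a whole; E.3c simply does not repeat it.
2. *The E.3c list describes the source measure.* The seven terms say what the Johns Hopkins measure explores. The guides are based on that measure and then adapted by stakeholder group, so the list does not fix their full content.
3. *The ethics clause governs modifications.* It concerns changes made to questions or probes, not what the guides in Rascal already contain. Its reference to constructs described earlier can also be read to take in Aim 2 and section C, which come before it in the same document.
4. *The section F list is not a test of what is collected.* It omits scalability and sustainability, which E.3c does name. If absence from this list meant absence of data, those two would be lost as well. The wording is anticipatory and codes may be added.
5. *Analysis (g) names no individual construct.* It is a generic mixed methods analysis of the implementation data. That none of the six lettered analyses names cost therefore says little, because (g) covers whatever the interviews yield.
6. *Other instruments are beside the point.* The plan promises to explore cost by interview. It does not promise a costing study or an economic evaluation, so the lack of resource-use fields in the ACASI or session forms breaks no commitment. The inventory in section G is also given as examples: "all data (e.g., ACASI data, CMF/TLFB data, implementation data) will be coded with ID numbers only".

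**The case for a change.** The strongest case for a change is that E.3c is the operative section. Aim 2 and section C list affordability or cost separately from feasibility and sustainability, so the protocol itself treats it as a distinct construct, and one should not assume that probes on feasibility will draw it out. An open codebook can only code what people were asked about or chose to say. The remedy would also be light: a few items for the 15 counselors and 15 officials, who are 30 of the 60 interviewees, and two aligned lists.

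Part of this stands. The sections do not match, and a reader with E.3c and section F alone would not learn that cost is to be explored. What does not stand is the step from mismatch to missing data. That step needs the guides to lack cost items, and the public document cannot show this either way. A light remedy does not make it necessary: the plan already commits the interviews to cost, so the edit would restate that commitment and leave the design and analysis as they are.

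**Conclusion.** No change to the plan follows. Affordability/cost is one of six promised implementation constructs and the only one not repeated in E.3c. Because section C already assigns it to the interviews, this is editorial unevenness between an overview and a procedures section, of the kind a study team settles when it writes and checks its guides.

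The consequence is confined to Aim 2, which is exploratory and rests on 60 purposively chosen interviewees. The difference in AUDIT change at 12 months, the 1:1 stratified randomization and the sample of 400 are unaffected.

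The conclusion assumes that the interview guides follow section C as well as E.3c. If they contained no cost or affordability questions, Aim 2 would fall short on one of its three targets. That would be a shortfall against a plan that already calls for the topic, and the ethics modification route in E.3c is available if questions had to be added. The wording mismatch is certain; a gap in data collection is not shown.

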## **B. STUDY PURPOSE AND RATIONALE**

Provide pertinent background information with references that are related to the need to conduct this study. If this is a clinical trial, the background should include both preclinical and clinical data. Be brief and to the point.

Refugees are at risk for unhealthy alcohol and other drug (AOD) use, particularly in protracted emergencies. In this application we define unhealthy AOD use as hazardous use, harmful use, and alcohol/substance use disorder and dependence. Among refugees, baseline risk for AOD use may increase for several reasons, including access to illicit substances (reduced drug enforcement policies and security), exposure to potentially traumatic events, and chronic adversity. Ongoing adverse environments such as refugee camps, are associated with lack of access to basic needs, limited livelihoods opportunities, boredom, marginalization, loss of resources, and mental health problems leading to the use of AOD as a coping mechanism. Studies have suggested that in conflict settings,

quantity and frequency of use tend to increase from the pre-conflict stage to peri- and post-conflict. Increase in use of one substance can also lead to initiation of new substances, resulting in more complex cases of polysubstance use.

In Mantapala refugee settlement in Zambia, the proposed study setting, unhealthy AOD use is reportedly common. In July 2019, UNHCR requested psychiatric clinical officers from local health facilities in Nchelenge, Zambia to do an assessment of mental health problems among refugees in Mantapala. The community-based convenience sample consisted of 200 people, of whom 35 (18%) had probable alcohol use disorder, mostly adult men and adolescents (male and female), and frequent cannabis use among people who were drinking alcohol. Reports from 7 refugee incentive workers and 17 representatives from 6 implementing agencies during an initial site visit indicated that unhealthy AOD use was associated with individual, family, and community consequences (injury, gender-based violence, diversion of livelihoods). Reports from the province of origin (Katanga, DRC) and host country (Zambia) have also found AOD use to be prevalent.

The proposed study will test an intervention package known as 'screening, brief intervention, and referral to treatment' (SBIRT). SBIRT systems are evidence-based for the treatment of unhealthy AOD use in non-humanitarian settings and can efficiently provide individuals with an appropriate level of care based on their symptom presentation and severity.  For example, individuals with hazardous AOD use but without a more severe disorder and without mental health comorbidities may be best served by a brief intervention (BI); for many of these individuals, a full course of a psychotherapy may not be necessary (i.e., inefficient use of limited resources). On the other hand, individuals with more severe AOD disorder or mental health comorbidities likely require more comprehensive treatment. In this trial we will provide BI or BI+psychotherapy commensurate with an individual's symptom presentation.

The interventions included in the SBIRT system are the Common Elements Treatment Approach-Brief Intervention (CETA-BI) and the full CETA psychotherapy (CETA). Previous randomized controlled trials have found CETA to be an effective treatment, including among refugees, for a range of mental and behavioral health problems, including depression, anxiety, trauma, and functional impairment. 15-17 CETA has recently been tested in Zambia and found to also reduce unhealthy alcohol use in addition to mental health problems and intimate partner violence. 17 CETA is a transdiagnostic approach, meaning that counselors trained in CETA are equipped with the ability to treat a range of co-occurring mental and behavioral health conditions. It was developed for use in low- and middle-income countries (LMIC) to facilitate lower cost and sustainability. CETA includes 9 cognitive behavioral elements found in most evidence-based psychological treatments. 18 CETA is 6-12 weekly one-hour sessions with flexibility depending on symptom severity. CETA-BI combines motivational interviewing skills with cognitive behavioral therapy to assist clients in considering changing their rates of AOD use. The intervention lasts 30-40 minutes and consists of 6 components including: 1) screening; 2) identifying the impacts of unhealthy AOD use; 3) talking about change and goal-setting; 4) understanding the primary reason for drinking; 5) skill building; and 6) referral for services. CETA-BI and CETA were previously found effective for AOD use and mental health problems within HIV care in Lusaka, Zambia. 19 CETA-BI and CETA have significant potential for adaptation and implementation in refugee settings but a rigorous RCT adapting and testing them in an SBIRT stepped-care approach among refugees is warranted.

All SBIRT components will be delivered by lay counselors. Counselors will already have been trained in the SBIRT interventions through our formative work in Mantapala (IRB AAAT1592). This enhances feasibility, scalability, and sustainability. Further, all aspects of the SBIRT are designed to be flexible: the

screening, the provision of the BI, and the referral for treatment and provision of full CETA can be done in the community and in locations where clients feel comfortable.

#### C. OVERVIEW OF STUDY DESIGN

Describe the methodology that will be used in this study, covering such factors as retrospective vs. prospective data collection, interventional vs. non-interventional, randomized vs. non-randomized, observational, experimental, ethnography, etc.

The study design involves a randomized controlled trial evaluating effectiveness (e.g., alcohol use, mental health; Aim 1) and implementation (e.g., scalability; Aim 2) of the SBIRT system of care for alcohol and other drug use problems in Mantapala refugee settlement in Luapula Province, which is located in northern Zambia. We will enroll 400 participants into the RCT; half will be randomly assigned to receive SBIRT and half will be randomly assigned to receive treatment as usual (TAU). We will evaluate self-reported alcohol, substance use, and mental health outcomes via audio computer-assisted self-interviewing (ACASI) at three timepoints: baseline, 6 months post-baseline, and 12 months post-baseline. We will conduct mixed methods interviews with a sub-sample of participants, SBIRT counselors, and humanitarian program and policy officials to explore implementation constructs of intervention acceptability, feasibility, appropriateness, and cost.

